## 7. DISCONTINUATION OF STUDY DRUG AND PARTICIPANT DISCONTINUATION/WITHDRAWAL

### 7.1. Discontinuation of Study Drug

In rare instances, it may be necessary for a participant to permanently discontinue (definitive discontinuation) the study drug. If the study drug is definitively discontinued, the participant should remain in the study to be evaluated for safety follow up. See the SoA (Section 1.3) for data to be collected at the time of discontinuation of the study drug and follow-up and for any further evaluations that need to be completed.

Participants should be considered for discontinuation from study drug if any of the following occur during the study:

- 1. Serious hypersensitivity reaction
- 2. Use of disallowed medication as defined in Section 6.5
- 3. Alexion or the Investigator deems it is necessary for the participant
- 4. Withdrawal of consent.

Participants who become pregnant must have study drug discontinued.

### 7.2. Participant Discontinuation/Withdrawal from the Study

All efforts should be made to ensure participants are willing to comply with study participation prior to conducting the screening procedures. The study staff should notify their site monitor and Alexion of all study withdrawals as soon as possible. The reason for participant discontinuation must be recorded in the source documents and eCRF.

If a participant withdraws consent, the assessments specified for the Early Termination (ET) visit (as shown in the SoA, Section 1.3) will be performed and Alexion and site monitor notified as soon as possible. Participants who withdraw from the study will not be replaced.

Participants should be permanently discontinued from ravulizumab treatment if any of the following occur during the study:

- Serious infusion reaction (such as bronchospasm with wheezing or requiring ventilator support or symptomatic hypotension) or serum sickness-like reactions manifesting 1 to 14 days after drug administration;
- Severe uncontrolled infection;
- Pregnancy or planned pregnancy; or
- If the Alexion Medical Monitor or the Investigator deems it is in the best interest of the participant.

The Investigator should speak with the Medical Monitor prior to discontinuing a participant's study treatment. If a participant is discontinued from study drug, the participant should be encouraged to return for the remainder of his or her scheduled protocol visits until starting a different complement-targeted therapy.

If a participant is discontinued from the study with an ongoing AE or an unresolved laboratory result that, in the opinion of the Investigator, is significantly outside of the reference range and
clinically significant (Section 10.3), the Investigator will attempt to provide follow-up until a satisfactory clinical resolution of the laboratory result or adverse event is achieved.

If a female participant is permanently discontinued from ravulizumab treatment due to pregnancy, the Investigator will attempt to follow-up until the outcome of the pregnancy (Section 10.4).

- A participant may withdraw from the study at any time at his/her own request or may be withdrawn at any time at the discretion of the Investigator for safety, behavioral, compliance, or administrative reasons. This is expected to be uncommon.
- If the participant withdraws consent for disclosure of future information, Alexion may retain and continue to use any data collected before such a withdrawal of consent.
- If a participant withdraws from the study, he/she may request destruction of any samples taken and not tested, and the Investigator must document this in the site study records.

# 7.3. Lost to Follow up

If a participant fails to return, or is otherwise unavailable, for a scheduled visit within the acceptable visit window (Section 1.3), the site study staff must make a reasonable attempt to contact the participant to determine the reason for missing the appointment.

Participants who fail to return for a scheduled visit must be contacted by the site's study staff to determine the reason for missing the appointment. As it is vital to obtain any participant's missing visit information to ensure the missed appointment was not due to an AE or potential relapse, every effort must be made to undertake protocol-specified safety follow-up procedures.

A participant will be considered lost to follow-up if he or she repeatedly fails to return for scheduled visits and is unable to be contacted by the study site.

The following actions must be taken if a participant fails to return to the clinic for a required study visit:

- The site must attempt to contact the participant and reschedule the missed visit as soon as possible and counsel the participant on the importance of maintaining the assigned visit schedule and ascertain whether or not the participant wishes to and/or should continue in the study.
- Before a participant is deemed lost to follow up, the Investigator or designee must make every effort to regain contact with the participant (where possible, 3 telephone calls and, if necessary, a certified letter to the participant's last known mailing address or local equivalent methods). These contact attempts should be documented in the participant's medical record.
- Should the participant continue to be unreachable, he/she will be considered to have withdrawn from the study.

Discontinuation of specific sites or of the study as a whole are handled as part of Section 10.1.8.

# 8. STUDY ASSESSMENTS AND PROCEDURES

- Study procedures and their timing are summarized in the SoA (Section 1.3).
- Immediate safety concerns should be discussed with Alexion immediately upon occurrence or awareness to determine if the participant should receive the study drug.
- Adherence to the study design requirements, including those specified in the SoA, is essential and required for study conduct.
- During Screening, eculizumab may be administered at the participant's home at the discretion of the Investigator and preference of the patient, in accordance with the local procedures and Standard Operating Procedures at the site. These visits will be conducted by a trained qualified staff member. During a home administration visit, all assessments will be performed according to the SoA (Table 1). Patients must return to the study site for any visit at which PD sampling (Day –57 and Day –29) is scheduled, as specified in the SoA (Table 1). In countries where local legislation does not allow infusions outside authorized study sites, the Investigators will be notified in writing that this provision is prohibited
- All screening evaluations must be completed and reviewed to confirm that potential participants meet all eligibility criteria. The Investigator will maintain a screening log to record details of all participants screened and to confirm eligibility or record reasons for screening failure, as applicable.
- Procedures conducted as part of the participant's routine clinical management (eg, blood count) and obtained before signing of the ICF may be utilized for screening or baseline purposes provided the procedures met the protocol-specified criteria and were performed within the time frame defined in the SoA.

## 8.1. Efficacy Assessments

### 8.1.1. Transfusions

Administration of a pRBC transfusion, including the hemoglobin result and symptoms that triggered the transfusion and the number of units transfused, will be documented in the eCRF.

### 8.1.2. Lactate Dehydrogenase and Other Disease-Related Laboratory Parameters

Blood and urine samples will be collected at the times indicated in the SoA (Section 1.3) and as indicated in Section 10.2.

The following disease-related laboratory parameters will be measured during the study (refer to Section 8.5 and Section 8.6 for PK/PD assessments):

- LDH
- free hemoglobin
- occult blood, urine
- haptoglobin

- reticulocyte count
- PNH RBC clone size evaluated by high-sensitivity flow cytometry (Borowitz, 2010)
- estimated glomerular filtration rate (calculated using the Schwartz formula)

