## 1. **PROTOCOL SUMMARY**

### 1.1. Synopsis

#### **Protocol Title:**

Phase 4, Single-Arm Study of Ravulizumab in Adult Participants with Paroxysmal Nocturnal Hemoglobinuria Currently Treated with High-Dose Eculizumab

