### Age

1. Participant must be 18 years of age or older, at the time of signing the informed consent.

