### **Medical Conditions**

- 1. History of major adverse vascular events (MAVEs) within 6 months of Day 1.
- 2. History of bone marrow transplantation.
- 3. History of *N. meningitidis* infection
- 4. History of unexplained, recurrent infection.
- 5. Active systemic bacterial, viral, or fungal infection within 14 days prior to study drug administration on Day 1.
- Presence of fever ≥ 38°C (100.4°F) within 7 days prior to study drug administration on Day 1.
- 7. History of or ongoing major cardiac, pulmonary, renal, endocrine, or hepatic disease (eg, active hepatitis) that, in the opinion of the Investigator or Alexion, precludes the participant's participation in an investigational clinical trial.
- 8. Unstable medical conditions (eg, myocardial ischemia, active gastrointestinal bleed, severe congestive heart failure, anticipated need for major surgery within 6 months of Day 1, coexisting chronic anemia unrelated to PNH) that would make them unlikely to tolerate the requirements of the protocol.
- 9. Hypersensitivity to the active substance or to any of the excipients.
- 10. Known or suspected history of drug or alcohol abuse or dependence within 1 year prior to the start of Screening.
- 11. Known medical or psychological condition(s) or risk factor that, in the opinion of the Investigator or Alexion, might interfere with the participant's full participation in the study, pose any additional risk for the participant, or confound the assessment of the participant or outcome of the study.
- 12. Clinically significant multiple or severe drug allergies, intolerance to topical corticosteroids, or severe post-treatment hypersensitivity reactions (including, but not

limited to, erythema multiforme major, linear immunoglobulin A dermatosis, toxic epidermal necrolysis, and exfoliative dermatitis).

- 13. Lymphoma, leukemia, myelodysplastic syndrome, or any malignancy within the past 5 years except for basal cell or squamous epithelial carcinomas of the skin that have been resected with no evidence of metastatic disease for 3 years.
- 14. Major surgery within 90 days prior to dosing on Day 1.

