#### 8.2.1. Physical Examinations

- A complete physical examination will include, at a minimum, assessments of the cardiovascular, respiratory, gastrointestinal and neurological systems. Height and weight will also be measured and recorded.
- An abbreviated physical examination will include, at a minimum, assessments of the skin, lungs, cardiovascular system, and abdomen (liver and spleen).
- Investigators should pay special attention to clinical signs related to previous serious illnesses.
- Additional physical examinations can be performed as medically indicated during the study at the Investigator's discretion.

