11.2. Laboratory Evaluations

Safety laboratory samples for hematology, chemistry, urinalysis, and coagulation will be collected by both central and local laboratory at timepoints specified in the schedule of assessments (see sections 1.3 and 10.2 of the protocol).

Descriptive statistics by visit will be presented for each central laboratory parameter and for changes from baseline (continuous variables), for the Safety set. Shift tables over time will be presented for all central laboratory values, where applicable, using normal, low, or high on the basis of normal range values. Individual participant plots as well as boxplots will be presented for the following central laboratory parameters: hemoglobin, haptoglobin, hematocrit, reticulocytes, LDH, bilirubin, direct bilirubin, creatinine, aspartate aminotransferase, alanine aminotransferase, and gamma-glutamyl transferase.

Furthermore, results of PNH clone during the course of the study will be summarized.

Clinical central laboratory samples that meet the definition of table top hemolysis (TTH) will be identified and all potassium, alanine aminotransferase, aspartate aminotransferase, magnesium, phosphorous, and LDH samples affected by TTH will be excluded from analysis of all efficacy and safety endpoints, with the exception that the LDH values will be used for the qualification of BTH. The TTH samples from the central laboratory will be defined as having serum potassium ≥ 6 mmol/L and LDH $\geq 2 \times$ ULN, and will be listed.

All central and local laboratory data will be presented in by-participant listings.

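### eGFR is specified by the Schwartz formula, a pediatric height-based equation with its constant unstated, in an adults-only trial (minor correction)

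*Protocol*

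**What the plan says.** Protocol Section 8.1.2 sits under the efficacy assessments. It opens its list with "The following disease-related laboratory parameters will be measured during the study", and the last item is "estimated glomerular filtration rate (calculated using the Schwartz formula". No constant, version, reference or reason accompanies the formula.

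The population is adult throughout. The title reads "Phase 4, Single-Arm Study of Ravulizumab in Adult Participants with Paroxysmal Nocturnal Hemoglobinuria Currently Treated with High-Dose Eculizumab", and the first inclusion criterion is "Participant must be 18 years of age or older, at the time of signing the informed consent".

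eGFR is not mentioned anywhere else:

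- Table 6 of the protocol (Appendix 2) lists creatinine but not eGFR.
- SAP 11.2 makes a general commitment, "Descriptive statistics by visit will be presented for each central laboratory parameter and for changes from baseline". Its named list for individual plots and boxplots includes "creatinine, aspartate aminotransferase, alanine aminotransferase, and gamma-glutamyl transferase" but not eGFR.
- SAP Section 14, which records departures from the protocol's planned analysis, mentions neither the formula nor the parameter.

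**The concern.** The method does not fit the population. The documents do not describe the Schwartz formula; what follows is general knowledge of the named method. It estimates filtration in children from height and serum creatinine. In adults, height does not track filtration in that way, and age and sex, which adult equations use, are absent. Two adults of equal height and creatinine get the same value at 30 and at 75 years. A man of 190 cm gets a value 8.6% higher than a man of 175 cm with the same creatinine (190/175 = 1.086).

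The unstated constant is a second gap. Two programmers could both follow Section 8.1.2 and report values a third apart (0.55/0.413 = 1.33).

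Protocol Section 2.2 describes renal dysfunction as common in PNH, and Section 8.1.2 classes eGFR as disease-related. A reader of the study report could reasonably treat a table of eGFR as evidence on whether renal function was maintained after the switch. At stake is whether that one parameter can be interpreted.

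**Working it through.** The plan states no eGFR value, constant or threshold, so there is no figure of its own to reproduce. The calculation is an illustration with assumed inputs; none of the numerical inputs comes from the documents.

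**Inputs (assumed)**

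- Schwartz constant k: 0.413 or 0.55, two commonly used values.
- Adult comparator: the 2021 creatinine-based CKD-EPI equation.
- Grid: a woman of 162 cm and a man of 176 cm; ages 20, 30, 45, 60, 75; serum creatinine (Scr) 0.6, 0.8, 1.0, 1.5, 2.0 mg/dL. That is 2 × 5 × 5 = 50 profiles.

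**Formulas** (mL/min/1.73 m²)

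- Schwartz = k × height (cm) / Scr
- CKD-EPI 2021 = 142 × min(Scr/κ, 1)^α × max(Scr/κ, 1)^-1.2 × 0.9938^age × 1.012 if female, with κ = 0.7 and α = -0.241 for women, κ = 0.9 and α = -0.302 for men

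**Absolute values: selected profiles**

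| Profile | Schwartz, k = 0.413 | Schwartz, k = 0.55 | CKD-EPI 2021 |
|---|---|---|---|
| Man, 20 y, Scr 1.0 | 73 (-34%) | 97 (-12%) | 110 |
| Man, 30 y, Scr 1.0 | 73 (-30%) | 97 (-7%) | 104 |
| Man, 45 y, Scr 1.0 | 73 (-23%) | 97 (+2%) | 95 |
| Man, 75 y, Scr 1.0 | 73 (-7%) | 97 (+23%) | 78 |
| Woman, 60 y, Scr 0.8 | 84 (-1%) | 111 (+32%) | 84 |
| Woman, 75 y, Scr 2.0 | 33 (+31%) | 45 (+74%) | 26 |

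The first and last rows are the extremes of the grid. For example, the last row is 0.413 × 162 / 2.0 = 33.5 against 25.6, a ratio of 1.31. The four rows for the man show the missing age term: his Schwartz value stays fixed while the adult equation falls from 110 to 78.

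**Absolute values: whole grid**

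| k | Range of relative difference | Profiles within 10% |
|---|---|---|
| 0.413 | -34% to +31% | 22 of 50 (44%) |
| 0.55 | -12% to +74% | 12 of 50 (24%) |

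**Change from baseline**

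Within one adult, height and k cancel, so the Schwartz ratio is baseline Scr divided by follow-up Scr. Age is held fixed here.

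- Man, Scr 0.6 to 0.9: Schwartz 0.6/0.9 = 0.667, a fall of 33%. Adult equation (0.9/0.6)^-0.302 = 1.5^-0.302 = 0.885, a fall of about 12%.
- Man, Scr 1.0 to 1.5: Schwartz again falls 33%. Adult equation 1.5^-1.2 = 0.615, a fall of about 39%.

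The direction agrees but the size does not. Schwartz overstates the fall at low creatinine and understates it above the adult equation's breakpoint.

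**What depends on eGFR**

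- Endpoints (Protocol Section 3, SAP Section 4): eGFR is not among them.
- Eligibility (Protocol Section 5.2): the renal criterion, "History of or ongoing major cardiac, pulmonary, renal, endocrine, or hepatic disease", turns on the opinion of the investigator or sponsor, with no eGFR threshold.
- Dosing (Protocol Section 6.1.1): by body weight.
- Subgroups (SAP 6.6): none planned.
- Sample size (Protocol Section 9.2): based on the breakthrough hemolysis proportion.

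**The case against.** The strongest case on the other side accepts that the formula is misnamed and disputes the consequence.

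- **Many values would be close.** This stands. A reader might infer that every reported eGFR would be wrong. The grid does not support that: 22 of 50 profiles agree within 10% at k = 0.413 and 12 of 50 at k = 0.55. The values are unreliable, because which ones are close depends on age, sex, creatinine and an unstated constant.
- **No specific eGFR output is planned.** This stands in part. SAP 11.2 does not name eGFR, and as a derived quantity it may not count as a central laboratory parameter. But the protocol says it will be measured, and SAP 6.1 says that all collected data and derived outcomes will be presented. Reporting it is the natural reading, and omitting it would drop a listed parameter without explanation.
- **Nothing turns on renal grouping.** This stands. A reader might infer that participants would be misclassified by renal function. No rule or analysis in the documents uses such a grouping.
- **Height and the constant cancel from percent change.** This is true, and it removes the height and constant problems for within-participant percent change. It does not repair absolute values, and the size of change still differs, as the 0.6 to 0.9 mg/dL example shows.
- **The magnitudes are assumed.** This stands. They show what the formula can do in adults; they do not measure any trial result.

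**Conclusion.** The point holds in a limited form. Section 8.1.2 is current text that assigns a pediatric height-based equation, constant unstated, to an adults-only trial, and nothing elsewhere corrects it. Absolute eGFR values and the size of changes from baseline would be unreliable by the margins shown above. Those margins rest on the assumed constants, the assumed adult profiles and CKD-EPI 2021 as comparator. Other choices would move the figures but would not give the formula an age or sex term.

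The harm is confined to one listed laboratory parameter. A reader might infer that the efficacy or safety conclusions are compromised; the documents do not support that, because no endpoint, eligibility rule, dosing rule, subgroup or sample-size figure uses eGFR. This is a minor correction.

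**What to change.** - **Protocol Section 8.1.2:** replace the Schwartz formula with a named adult creatinine-based equation and its version, for example CKD-EPI 2021.
- **SAP 11.2:** use that equation wherever eGFR is reported. One sentence saying whether eGFR will be summarized would settle the present silence; a new dedicated analysis is not required.
- **SAP Section 14 or the clinical study report:** record the change. Protocol Section 9.4 allows changes to analysis methods that leave the primary and secondary objectives and study conduct untouched to be described in the report without an amendment.

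The cost is a phrase in the protocol and a derivation line in the SAP. Creatinine is in Table 6 and is drawn with chemistry at screening and at every treatment-period visit. Age and sex are collected as demographics (SAP 7.2). Any values already derived can be recomputed retrospectively, with no added visit, sample or data field.

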### 8.1.3. Paroxysmal Nocturnal Hemoglobinuria Symptomatology

The Investigator or designee will record for each participant the presence or absence of the following signs and symptoms of PNH: fatigue, chest pain, hemoglobinuria, abdominal pain, dyspnea, dysphagia, erectile dysfunction, and red/dark urine or hemoglobinuria.

### 8.1.4. Major Adverse Vascular Events

Major adverse vascular events will be assessed as part of the planned evaluation for AEs as described in Section 8.3.

The description of the MAVE including the method of diagnosis (eg, magnetic resonance imaging, ultrasound, angiogram), date of diagnosis, and date resolved (or ongoing) will be collected on the eCRF as part of the participant's medical history (prior to baseline).

A MAVE is defined as follows:

- Thrombophlebitis/deep vein thrombosis
- Pulmonary embolus
- Myocardial infarction
- Transient ischemic attack
- Unstable angina
- Renal vein thrombosis
- Acute peripheral vascular occlusion
- Mesenteric/visceral vein thrombosis or infarction
- Mesenteric/visceral arterial thrombosis or infarction
- Hepatic/portal vein thrombosis (Budd-Chiari syndrome)
- Cerebral arterial occlusion/cerebrovascular accident
- Cerebral venous occlusion
- Renal arterial thrombosis
- Gangrene (nontraumatic; nondiabetic)
- Amputation (nontraumatic; nondiabetic)
- Dermal thrombosis
- Other, specify

## 8.2. Safety Assessments

Planned time points for all safety assessments are provided in the SoA (Section 1.3).

#### 8.2.1. Physical Examinations

- A complete physical examination will include, at a minimum, assessments of the cardiovascular, respiratory, gastrointestinal and neurological systems. Height and weight will also be measured and recorded.
- An abbreviated physical examination will include, at a minimum, assessments of the skin, lungs, cardiovascular system, and abdomen (liver and spleen).
- Investigators should pay special attention to clinical signs related to previous serious illnesses.
- Additional physical examinations can be performed as medically indicated during the study at the Investigator's discretion.

## 8.2.2. Vital Signs

- Oral temperature, pulse rate, respiratory rate, and blood pressure will be assessed.
- Blood pressure and pulse measurements will be assessed with an automated device. Manual techniques will be used only if an automated device is not available.
- Vital sign measurements will be taken after the participant has been resting for at least 5 minutes and will include systolic and diastolic blood pressure (millimeters of mercury [mmHg]), heart rate (beats/minute), respiratory rate (breaths/minute), and temperature (degrees Celsius [°C] or degrees Fahrenheit [°F]). On dosing days, vital signs will be taken before study drug administration.

